## LIST OF ABBREVIATIONS AND RELEVANT DEFINITIONS

ABR	ABR form (General Assessment and Registration form) is the application form
	that is required for submission to the accredited Ethics Committee (ABR =
	Algemene Beoordeling en Registratie)
AE	Adverse Event
AR	Adverse Reaction
CA	Competent Authority
ССМО	Central Committee on Research Involving Human Subjects
CV	Curriculum Vitae
DSMB	Data Safety Monitoring Board
EU	European Union
EudraCT	European drug regulatory affairs Clinical Trials GCP Good Clinical Practice
IB	Investigator's Brochure
IC	Informed Consent
IMP	Investigational Medicinal Product
IMPD	Investigational Medicinal Product Dossier
METC	Medical research ethics committee (MREC); in Dutch: medisch ethische toetsing
	commissie (METC)
(S)AE	Serious Adverse Event
SPC	Summary of Product Characteristics (in Dutch: officiële productinfomatie IB1-
	tekst)
Sponsor	The sponsor is the party that commissions the organisation or performance of the
	research, for example a pharmaceutical
	company, academic hospital, scientific organisation or investigator. A party that
	provides funding for a study but does not commission it is not regarded as the
	sponsor, but referred to as a subsidising party.
SUSAR	Suspected Unexpected Serious Adverse Reaction
Wbp	Personal Data Protection Act (in Dutch: Wet Bescherming Persoonsgevens)
WMO	Medical Research Involving Human Subjects Act (Wet Medisch-wetenschappelijk
	Onderzoek met Mensen

## SUMMARY

Rationale: Nowadays, many mental health care organizations measure their patient's progress through routine outcome monitoring. The way that progress is measured and the way therapists are provided with feedback on their patient's progress strongly differs between organizations. The question is whether all methods are as effective, and there is surprisingly little research on the effectiveness of routine outcome monitoring available. Research in the United States shows that providing feedback to therapists based on a prediction model, can improve patient outcome, especially for those patients that are not progressing well in treatment (o.a. Lambert, 2007). The prediction model that was used in the studies by Lambert was calculated based on the initial severity in patient disfunctioning, measured with the Outcome Questionnaire (OQ). Lambert and colleagues conducted five randomized controlled trials on the effectiveness of feedback based on the prediction model en found that in the 'not on track' group (patients that were not progressing well) treatment outcomes were significantly better in the experimental group than in the no feedback control condition. In the 'on track' group, the feedback did not have an effect on outcome. In the Netherland, a prediction model for Dutch patients was predicted, based on almost 2000 patients in four mental health care organizations. Our model uses the initial severity of patients disfunction, as well as patients' expectancies on treatment outcome as predictors for progress. Results showed that this was also a significant predictor for progess in the data that was collected.

**Objective**: In this study, two forms of feedback and one control condition are compared: \* Control group: the therapist gets no feedback.

\* Outcome monitoring feedback: the therapist gets feedback on the patients progress in a progress chart.

\* Complex feedback based on the Dutch prediction model: the therapist gets a progress chart that compares the patient's actual progress with the expected treatment response. Main questions:

1. Does providing feedback to therapists improve treatment outcome?

2. Does providing feedback based on the prediction model lead to better outcomes than progress feedback alone?

Secundary questions:

1. How well can therapists predict their patient's progress?

2. Are there differences between therapists in treatment outcomes and is this related to the way they use the feedback?

**Study design:** A 2-year randomized controlled clinical trial on the effectiveness of feedback interventions for therapists

**Study population:** The study population consists of psychiatric patients between 18 and 65 years that apply for outpatient individual psychiatric treatment in one of the three participating treatment facilities. Patients with psychotic disorders, a current crisis, a high risk of decompensation, a current severe manic episode or insufficient mastery of the Dutch language in reading and speaking are excluded from participating in the study. Patients can have supplement treatments beside the individual treatment and stay in the study, as long as

the individual treatment remains the main treatment. Patients are excluded from the study if individual treatment is not their main treatment.

**Intervention (if applicable)**: The intervention consists of providing feedback to therapists on their patients' progress. In the outcome monitoring feedback condition the therapist gets feedback on patient progress in progress charts and tables. The progress of the patient can be viewed by the therapist at all times, by logging on to the feedback system (RequestXL), but is also actively provided by e-mail at session 1, 3, 5, 10 and 15.

In the complex feedback condition with prediction model the actual treatment course (based on the OQ scores) of the patient is compared with the predicted treatment course. The expected treatment course is calculated by a formula. The progress of the patient can be viewed by the therapist at all times, by logging on to the feedback system (RequestXL), but is also actively provided by e-mail when the patient is not progressing well. The therapist then receives an e-mail with high urgency.

In the complex feedback condition feedback is also provided on the ASC. The ASC is administered when the patient goes off track (through the 75% negative bound of the confidence interval around the predicted treatment course) and measures the therapeutic alliance, motivation, social support and life events. The ASC is combined with so called Clinical Support Tools, a set of Microsoft Word documents that provide practical tips on improving the therapeutic alliance, motivation and social support. The practical tips are based on a literature review on these topics.

**Main study parameters/endpoints:** The primary outcome measure of the study is patients' disfunctioning on the Outcome Questionnaire. Mores specifically, the progress that the patient makes during treatment. The results will be analysed using multilevel analysis, which has the advantage of being able to handle missing data really well. Therefore, data from all patients, including those that dropped out of treatment or dropped out of the study can be used in analysis.

# Nature and extent of the burden and risks associated with participation, benefit and group relatedness:

Burden: The burden for the patient consists of completing a 5 minute questionnaire before each treatment session, for a maximum of 15 times. After the research period (end of treatment or after 15 session) they will get two follow-up measures after 3 and 6 months. The average treatment duration for outpatient indivual treatment was around 9 sessions in a previous study at one of treatment settings. If patients go off track, they are asked to complete an addition questionnaire, that also takes about 5 minutes to complete. In addition to the self-report questionnaires, patients are getting a diagnostic interview that takes approximately 1 hour.

The burden for the therapist consist of completing brief questionnaires during the treatment of a participating patient (total burden around 10 minutes) and completing a longer questionnaire once every 6 months (about 20 minutes per administration, total of 5 administrations).

Risks: The risks for both the patient and the therapist are minimal.

#### 1. INTRODUCTION AND RATIONALE

A large body of research, performed over 40 years, has demonstrated the general effectiveness of psychological treatments (Lambert & Ogles, 2004). However, while treatment is beneficial for many patients, not all patients profit from therapy. In randomized controlled clinical trials, where treatment is provided under more or less optimal conditions, an average of 67% of patients is statistically reliably improved at the end of treatment. In clinical practice, the success rates are much lower: in an American national database of more than 6000 patients, only 35% of the patients was improved (Hansen, Lambert, & Forman, 2002).

Riemer & Bickman (2003) consider feedback interventions a promising approach to improve clinical practice. According to them, clinicians need to have more systematic and reliable information about the status of their patients, so that they are capable of adjusting their treatment. Literature from psychology, educational science and medicine shows the effectiveness of feedback interventions (e.g. Kluger & DeNisi, 1996, 1998; Jamtvedt et al., 2006; Hattie & Timperley, 2007; Veloski et al., 2006). A general meta-analysis by Kluger & DeNisi (1996) showed an average effect size of 0.38 for feedback interventions. More specifically tailored to the effectiveness of health status feedback to professionals, a meta-analysis by Sapyta (2004, in Sapyta, Riemer, & Bickman, 2005) found an average effect size of 0.21. Further analysis showed that feedback on 'flagged patients' (those not progressing well in treatment) had an average effect size of 0.31, while there was no significant feedback effect for the 'non-flagged' samples.

In psychotherapy the research group of Michael Lambert has published five controlled studies in which therapists received feedback about a patient's improvement through the use of progress charts and warnings about patients who were not demonstrating the expected treatment response (Hawkins, Lambert, Vermeersch, Slade, & Tuttle, 2004; Lambert, et al., 2002; Lambert, et al., 2001; Whipple, et al., 2003)Harmon et al., 2007. Results showed that patients at risk for treatment failure in the feedback condition showed significantly more improvement than at risk-patients in the no-feedback control condition. This effect was even stronger when feedback was combined with a clinical support tool. The effect sizes for the difference between patients at risk in the various feedback conditions and control conditions ranged from 0.34 to 0.92. Feedback had no significant effect in the non-flagged samples (Lambert, 2007). Other research groups have focused mainly on calculating an expected treatment response to signal patients at risk for treatment failure (Lueger, et al., 2001; Lutz, et al., 2006)(e.g. Lutz, Martinovich & Howard, 1999), but in psychotherapy Lambert and colleagues are the only ones that have studied the effect of feedback in a controlled design.

In order to get an idea as to why providing therapist with feedback works, Hannan et al (2005) performed a study in which therapists were asked to rate their patients' progress and predict patient outcome in a period of three weeks. The therapist's predictions were compared with a statistical prediction model and with actual outcome. Therapists tended to overestimate the percentage of positive outcomes and underestimate the percentage of patients that did not change or deteriorated during treatment. In 332 patients, 26 patients actually deteriorated, of which the statistical procedure identified 77% correctly, while

therapists identified only 0.04% of the patients correctly as a treatment failure. This study shows that therapists might not be very good in predicting their patients' progress, when it comes to predicting poor outcomes. By contrast, in a randomized controlled trial comparing two treatments for borderline personality disorders Spinhoven, Giesen-Bloo, Van Dyck & Arntz (2008) found that therapists and assessors could accurately predict indices of outcome above and independent of patient characteristics. Surprisingly few studies have been performed in this area, but the two available studies seem to show mixed results.

The studies performed by the research group of Lambert are not without limitations. Most of the studies have been conducted in the university counseling center, where students are the main treatment population (Lambert, 2007). Only one of the studies has been conducted in a community outpatient setting (Hawkins et al., 2004). Another critique has been that hardly any replications were outside the research group of Lambert; the only one being in a 30-day inpatient treatment in Switzerland (Berking, Orth & Lutz, 2006). Part of the reasons there have been so few replications outside of Lambert's group is that in order to replicate the studies by Lambert, one needs a prediction model to identify the off-track patients. If patients deviated too from the expected treatment response predicted by the model, and exceed the error bound around this prediction, they are considered to be off-track. Developing a prediction model for expected treatment response takes a substantial amount of effort and most research groups have either not invested in that, or have not been able to get enough data yet to develop a model. Fortunately, there is a prediction model available for Dutch mental health care (de Jong et al, in preparation).

One of the issues that is important in feedback studies is whether merely providing the therapist with feedback is enough. According to general theories of feedback, when a person receives feedback a comparison is made between the content of the feedback and a goal or standard (Kluger & DeNisi, 1996). In clinical practice, therapists are usually motivated to achieve improvement or recovery in their patients. When presented with feedback, for instance patient progress charts, a comparison is made between the goal (progress towards recovery) and the feedback (progress so far). The result of this feedback-standard comparison creates a feedback sign – a positive or negative evaluation of one's performance relative to the goal. When a discrepancy is noted, people are motivated to reduce it. Following this line of thinking, it makes sense that feedback does not work in non-flagged case, as there is no discrepancy in these cases, so therapists are not motivated to change their behavior.

The effects of feedback are complex and there are numerous factors that influence the impact of feedback. In feedback studies in clinical practice, especially the factors associated with the recipient of the feedback, the therapist, seem important. If a therapist does not look at the feedback, or does not take it seriously, the feedback intervention might loose its effect. Feedback is more likely to be accepted if it comes from a source that has credibility, a combination of expertise and trustworthiness, and has personal relevance to the receiver (Clairborn & Goodyear, 2005; Sapyta, et al., 2005). Another variable that seems important in whether external feedback will be accepted by the recipient is the feedback preference or propensity of that person. Herold and colleagues (Herold & Fedor, 2003)(Herold, Parsons &

Rensvold, 1996; Herold & Fedor 1998) report that some people have greater preference for externally mediated feedback than others. They refer to this preference as having an *external feedback propensity*. Sapyta et al. (2005) stress that goal commitment is another important recipient variable. Goal commitment is the amount of interest a person has in accomplishing a goal, even if it requires time and effort. Self-regulation theories propose that a discrepancy between a current actual and a desired goal state causes a person to change behavior only if the person is both committed to the goal and aware of the discrepancy. A person is committed to a certain goal mainly if the goal is attractive to him and if he believes it is reasonable for him to accomplish the goal.

## 2. OBJECTIVES

Primary Objectives:

- 1) Does providing therapists with feedback about their patients improve patient outcomes?
- 2) Does providing feedback based on an expected treatment response result in better outcomes than routine outcome monitoring feedback?

Secondary Objectives:

- 1) Can therapists accurately predict their patient's progress, with or without getting feedback?
- 2) Are therapists' feedback propensity and goal commitment predictive of better outcomes in the feedback conditions?

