## 4. STUDY POPULATION

## 4.1 Population (base)

*Patients.* Approximately 800 patients between 18 and 65 years, that apply for individual psychotherapy or psychological treatment at one of the three research locations (Schagen, Deventer, Twello), will be asked to participate in the study. *Therapists.* Therapists are psychotherapists, psychologists or psychiatric nurses that work

at the three research locations. Trainees will be excluded from the study. Approximately 50 therapists will be included in the study.

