## 4.4 Sample size calculation

Performing an a priori power analyses for multilevel analysis is complicated, because one has to have a good estimate of the variance components in advance and these are usually unknown, especially for three level models and three research conditions (de Jong, Moerbeek & Van der Leeden, 2009). An a priori power analysis was performed for two research conditions, based on the variance components of previously collected data, which resulted in approximately 4 patients per therapist, and 50 therapists participating for a power of 0.80, which is generally considered to be sufficient. However, this analysis was performed with an intended moderate effect (Cohen's d = 0.50), whereas feedback metaanalysis shows a small effect (Cohen's d=0.30). Also, in the current study we have three research conditions, which is considerably more complicated to model. The difference between the two feedback conditions is most likely smaller than d=0.30. Another thing that needs to be considered is that the effect only applies to the "not on track" group. As this group consists of approximately 25% of the total patient group and we cannot identify this group beforehand, the number of patients that need to be included in the study needs to be four times as large as the results from the a priori power analysis.

A traditional a priori power analysis was performed in G\*Power 3.0.10 for F tests with repeated measures, three research groups, three repeated measures, a power coefficient of 0.80, an  $\alpha$  of 0.05, and a correlation of 0.70 between the repeated measures. This resulted in a needed sample size of 90 not on track patients. The total sample size needed would then be 360 patients. This analysis does not take into account that patients are nested within therapists and therapists will explain part of the variance. We know from a previous study that the intraclass correlation was 0.18 at the therapist level. A rule of thumb to correct for the variance at the therapist level is to use the formula for the design effect:  $1 + (k-1)^{*icc}$ , with k being the number of patient per therapist, we would get a design effect of: 1 + 3 \* 0.18 = 1,54. This means that  $1.54^{*}360 = 554$  patients need to be included in the study. As we expect that some of the data will not be valid, the number of 600 patients was chosen as targeted *N*.

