## 5. TREATMENT OF SUBJECTS

## 5.1 Investigational product/treatment

In the ETR feedback condition, the therapist will receive feedback about the patient's progress, bases on an expected treatment response model. The ETR model is based on data collected in three different mental health care organizations in the Netherlands (de Jong et al, in preparation). Therapists receive an alert when the patient deviates from the expected track. An error bound around the expected treatment response for the patient indicates when the therapist is signals. If 75% failure boundary is crossed by the patient, the therapist receives an orange warning signal, indicating that the patient has an increased chance of treatment outcome. If the 95% failure boundary is crossed, the therapist receives a red warning signal, indicating that the patient is most like to have poor treatment outcome if he or she continues on the current track. When the patient signals orange or red, the Assessment for Signal Clients questionnaire will be administered to the patient, and the therapist will receive feedback about the scores on the ASC, in addition to the scores on the OQ-45.

In the ROM feedback condition, feedback is given in the form that most routine outcome monitoring feedback is being provided. The therapist gets a graph of the patient's progress after session 1, 3, 5, 10 and 15. In the graph, the patient's progress on the OQ-45 is monitored. The therapist receives feedback on the OQ total score, the subscale scores and the critical items.

In the control condition, therapists will receive no feedback about their patient's progress. All therapists can be in all three conditions, as randomization takes place at the patient's level.

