#### **Procedure**

All patients that asked to participate in this study will be interviewed with the MINI Plus as part of the standard intake procedure. After patients agree to participate the research assistant will adminster the SCID-II PQ. As from start of treatment, participants will be asked to complete the OQ-45 before each session, for a maximum of 15 sessions and/or one year. In addition, the OQ-45 will be administered 3 and 6 months after treatment (or study) termination. In the ETR feedback condition, patients will fill out the ASC when they are going off track. In the ROM feedback condition and control condition, patients will fill out the ASC when they would have signalled, but the therapist will receive no feedback on how the patient responded.

Therapists will be asked to complete the EOQ on each of their patients at sessions 1, 5, 10 and 15 or the end of treatment, if this is within 15 sessions. The UOF will be administrated after sessions 5, 10 and 15 or the end of treatment. To measure therapists' attitude towards getting feedback, the CFITUS will be administered before the start of the study, after six months, after one year and after a year and a halve. At the first administration, before the start of the study, the EFPS and GSE will be filled out by the therapists as well.

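### Secondary objective 2 asks whether therapist traits predict outcome in the feedback arms, whereas the rationale asks whether those traits change the effect of feedback; a trait that is only prognostic can be mistaken for one that makes feedback work

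*Protocol*

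**What the plan says.** In Protocol section 2, secondary objective 2 asks whether two therapist traits, feedback propensity and goal commitment, are "predictive of better outcomes in the feedback conditions". Secondary objective 1, directly above it, expressly covers therapists' predictions both with and without feedback; objective 2 names only the feedback conditions.

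Section 1 gives the reason for studying these traits. It describes characteristics of the recipient that alter the impact of feedback, and says that the intervention may lose its effect when a therapist ignores the feedback or does not take it seriously. It adds that a noticed discrepancy changes behaviour only in someone committed to the goal.

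On the design, section 5.1 states: "All therapists can be in all three conditions, as randomization takes place at the patient's level". It also states: "In the control condition, therapists will receive no feedback about their patient's progress". Section 6.3 (Procedure) schedules the therapist measures: "the CFITUS will be administered before the start of the study, after six months, after one year", and once more after a year and a half. The propensity scale is completed at the pre-start administration.

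Section 8.2 describes a three-level model with two condition dummies and initial severity as covariate. It names no therapist trait and no trait-by-condition term.

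**The concern.** The rationale concerns a difference in differences: is the gain from feedback over no feedback larger for therapists who score high on the trait? The objective concerns a single slope, that of outcome on trait among patients whose therapist receives feedback. That slope is the sum of the trait's general relation to outcome and any modification of the feedback effect. Without patients treated under no feedback, the two parts cannot be separated.

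Two wrong conclusions are possible. If committed or feedback-minded therapists obtain better results anyway, the trial may report that they profit from feedback when they do not. If the trait goes with poorer results in general, a real gain from feedback may be cancelled and missed. Either would misinform advice on which therapists benefit from such a system. The primary comparisons are not affected.

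**Working it through.** **Plan's own figures.** The protocol states no number for this objective. Its sample-size arithmetic reproduces (90 × 4 = 360; 1 + 3 × 0.18 = 1.54; 1.54 × 360 = 554.4) but does not bear on the point.

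**Inputs from the protocol**
- Therapist intraclass correlation, section 4.4: "We know from a previous study that the intraclass correlation was 0.18 at the therapist level".
- Number of therapists, section 4.1: "Approximately 50 therapists will be included in the study".
- Total sample, section 4.4: "the number of 600 patients was chosen as targeted" N. This gives 600/50 = 12 patients per therapist, of whom two-thirds, 8, fall in the two feedback arms.
- The design effect in section 4.4 uses 4 patients per therapist instead, which gives 4 × 2/3 = 2.67 in the feedback arms. Both caseloads are shown.

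**Assumption not in the protocol.** The correlation r between trait and general therapist effectiveness, or equivalently the share R² = r² of therapist variance that the trait explains. A range is shown.

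**Structure.** Let outcome have total SD 1, scored so that higher is better, and let the trait be standardised. Let m be the true modification.
- Slope in feedback arms = r√0.18 + m
- Slope in control = r√0.18
- Difference = m

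With m = 0, the spurious feedback-arm slope at r = 0.2, 0.3 and 0.5 is 0.08, 0.13 and 0.21 SD per SD of trait.

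**How often the feedback-arm slope is significant when m = 0.** Regress 50 therapist means on the trait:
- variance of a mean V = 0.18 + 0.82/n
- squared correlation ρ² = 0.18·R²/V
- noncentrality λ = 50·ρ²/(1 − ρ²), referred to F(1, 48), two-sided 5%

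| Feedback patients per therapist (n) | V | R² | ρ² | λ | Significant |
|---|---|---|---|---|---|
| 8 | 0.2825 | 5% | 0.032 | 1.65 | 24% |
| 8 | 0.2825 | 10% | 0.064 | 3.40 | 44% |
| 8 | 0.2825 | 25% | 0.159 | 9.47 | 85% |
| 2.67 | 0.4875 | 5% | 0.018 | 0.94 | 16% |
| 2.67 | 0.4875 | 10% | 0.037 | 1.92 | 27% |
| 2.67 | 0.4875 | 25% | 0.092 | 5.08 | 60% |

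**Check by simulation** (4,000 trials per row, 50 therapists, each patient allocated at random to one of three arms, m = 0). The contrast compares feedback with control patients of the same therapist.

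| Patients per therapist | r | Feedback-arm slope significant | Trait-by-feedback contrast significant |
|---|---|---|---|
| 12 | 0 | 4.5% | 4.4% |
| 12 | 0.2 | 19% | 4.3% |
| 12 | 0.3 | 39% | 5.4% |
| 12 | 0.5 | 82% | 5.1% |
| 4 | 0 | 5% | 4.9% |
| 4 | 0.2 | 13% | 5.4% |
| 4 | 0.3 | 23% | 4.8% |
| 4 | 0.5 | 56% | 4.7% |

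**The reverse error** (12 patients per therapist, true m = 0.20). At r = −0.47, r√0.18 = −0.20, so the feedback-arm slope averages 0.00 and is significant in 5% of trials. The contrast averages 0.20 and is significant in 64%.

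**Price of the contrast** (m = 0.20, r = 0, 12 per therapist). Power is about 66%, against 73% for the feedback-arm slope.

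**Therapists without a control patient.** Section 6.2 describes allocation as completely random and mentions no stratification by therapist. The chance of having none is (2/3)⁴ = 20%, about 10 of 50 therapists, at 4 patients each; at 12 it is (2/3)¹² = 0.8%, fewer than one therapist.

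**Limits.** Both calculations use therapist means of a single outcome, not the random-slope model of section 8.2 adjusted for initial severity. Section 4.4 does not say whether 0.18 refers to level or to rate of change.

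**The case against.** The objective is a research question, not a model. A reader might infer that the protocol fixes an analysis that leaves out the control patients. It does not: section 8.2 says nothing about therapist traits, and section 6.1.3 lists therapist factors without tying them to particular arms. The phrase can also be read as naming where the trait is expected to matter, which would agree with the Introduction. A statistical analysis plan that is not shown may contain the interaction, and its absence from the protocol is not a fault. This part stands, so the point concerns the wording of the objective.

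The percentages are also not false positives for the literal question. In the assumed data the trait does predict outcome. They become errors when the result is read as profit from feedback, which is the reading that the Introduction invites. At r = 0 there is no excess, and the protocol gives no value of r.

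Two further inferences are tempting but unsupported. One is that every therapist will treat patients in all three arms: section 5.1 says only that they can. The other is that goal commitment will be taken from later administrations, after exposure to feedback: a pre-start value is scheduled, and no passage says that later ones will be the predictor.

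Finally, the control patients are not a perfect reference. Therapists are unblinded and may carry habits learned from feedback over to them, which would dilute the contrast. This limits the remedy, but it does not make the feedback-arm slope evidence on who benefits.

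**Conclusion.** The point holds as a mismatch between objective and rationale. Secondary objective 2, taken as worded, cannot separate a therapist who does better in general from one who profits from feedback, and it can err in either direction. With no true modification, an intraclass correlation of 0.18 and 50 therapists, the chance of a significant feedback-arm association is about 24% to 85% at 12 patients per therapist and 16% to 60% at 4, if the trait explains 5% to 25% of therapist variance. These shares are assumptions. The documents do not show that the error will occur, only that the wording leaves it open. The matter is confined to one secondary objective; the primary objectives and the sample size are untouched.

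**What to change.** Reword secondary objective 2, for example: Do feedback propensity and goal commitment, measured before the start, modify the effect of feedback versus control? Test it with trait-by-condition terms, and their interaction with session, in the three-level model of section 8.2 using all three arms. Label the analysis exploratory.

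Naming the pre-start value also settles which measurement counts. Section 6.3 has the propensity scale in the six-monthly questionnaire in one place and at the first administration in another.

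The cost is one reworded sentence and the interaction terms; no new data are needed. The downsides should be stated with the result: lower precision (about 66% against 73% power for 0.20 SD at 12 patients per therapist), therapists without control patients if caseloads are small, and possible dilution by carry-over to the same therapist's control patients.
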